1.0 Introduction and Background

The Centers for Disease Control (CDC) estimates 1.9% of the estimated 16 million surgical procedures each year in the United States are complicated by a surgical site infection (SSI). The overall incidence of SSI with hysterectomy is between 1-2 %. [1,2]

Surgical site infections are classified as follows:

A 2011 study of postoperative surgical patients (general and vascular surgery) identified that SSI resulted in \$10,000 of excess hospital costs and prolonged hospital stay. [3] **In endometrial cancer patients, SSIs accounted for a \$5447 median increase in the 30-day cost of care.[4]** A recent article in AJOG 2017 noted SSI rates of 2% associated with hysterectomy with an added cost of \$5000 per case. [5] **Approximately 2/3 of gynecologic SSI are superficial incisional infections.[6]**

The Centers for Disease Control developed a Surgical Wound Classification system as outlined. This designed as a risk model for (SSI). As noted with an increase in the class there is an increase in the potential for infection.

Secondary versus Tertiary Wound Closure in High Risk
Gynecologic Abdominal Surgical Incisions
CCCWU # 04418

Surgical Wound Classification

Wound Class	Definition	Examples	Reminders
Class I Clean	
 ► Operative wound clean ► Non-traumatic, with no inflammation encountered ► No break in technique ► Respiratory, gastrointestinal and genito-urinary tracts not entered ► Caesarean Section, elective, no pre-rupture of membranes or trial of labor 	
 ► Vascular Procedures ► Neurological procedures (inflamed II, infected III) ► Endocrine procedures ► Eye surgery (inflamed II, foreign body III, infected III) ► Orthopedic procedures (unless: trauma III, old wound IV, inflammation II) ► Penile prosthesis ► Skin (mastectomy, lumpectomy, lesions, lipoma, cosmetic, I&D IV, old wounds III, inflamed III, infected IV) ► Exploratory Lap (no bowel involvement II) ► Miscellaneous procedures (lymph node excision/Bx unless inflamed III or infected IV, splenectomy, tenckhoff cath unless replacement II) 	

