Clean	No hollow viscus entered Primary wound closure No inflammation No breaks in aseptic tech Elective procedure	1 – 3%	
Clean contaminated	Hollow viscus entered but controlled No inflammation Primary wound closure Minor breaks in aseptic tech Bowel prep preop	5-6%	
Contaminated	Uncontrolled spillage from viscus Inflammation apparent Open,traumatic wound Major break in aseptic tech	20 – 25%	
Dirty	Untreated, uncontrolled spillage Pus in op wound Open suppurative wound Severe inflammation	30 – 40%	

Specifically related to gynecologic surgery, hysterectomy would be a clean contaminated or class II wound. Gross spillage from the gastrointestinal tract would be considered a contaminated or class III wound. A perforated viscus or abscess requiring surgery would be considered a dirty/infected or class IV wound. Prophylactic antibiotics are indicated for class II and III wounds; therapeutic antibiotics are necessary for class IV wounds.

Within the group of class II wounds (hysterectomy), there are a subset of patients in which there are factors that increase the risk of SSI above baseline. These include:

- a. Hyperglycemia,
- b. Smoking,
- c. Obesity (BMI \geq 30),
- d. Depth of subcutaneous tissue \geq 3 cm,
- e. Coexistent infection at a remote body site,
- f. Vaginal colonization (bacterial vaginosis),
- g. ASA status > 2,
- h. Immunodeficiency (chronic steroids, chemotherapy), and
- i. MRSA.

Numerous measures have been proved and/or recommended to decrease postoperative infection.

1. Preoperative Measures

- a. Treat remote infections
- b. Clippers if shaving needed
- c. Serum glucose control < 200 mg/dl
- d. Antimicrobial bath/shower
- e. Chlorhexidine abdominal/vaginal prep (70%/4%)
- f. Antibiotic prophylaxis

2. Intraoperative Measures

- a. Surgical technique
- b. Preventing hypothermia
- c. Appropriate re-dosing of prophylactic antibiotics
- d. Prevention of dead space and incisional seromas

Wound management techniques after fascial closure to address reduction in incisional infections especially in high risk class II and class III/IV wounds have included the following:

- Primary closure with subcutaneous drains and possibly incisional vacuum assisted closure device (VAC) for 3-4 days,
- Secondary closure with wound packing and dressing changes 2-3 times daily or VAC placement with changes 2-3 times weekly, and
- Tertiary or delayed primary closure.

Three techniques of wound treatment

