2.0 Objectives

2.1 Primary Objective

2.1.1 To compare the percentage of patients whose wound remained closed on postoperative day #30 after tertiary closure compared to historical controls who underwent secondary wound closure. We are primarily looking at time to wound closure. We will be able to abstract this information from the postoperative clinic visit notes from patients in the "historical control" cohort. We will identify 20 patients with characteristics described in the inclusion criteria of this study who underwent laparotomy with secondary wound closure during the calendar year 2018.

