4.3 Experimental Methods

4.3.1 Patients will undergo standard of care surgery.

4.3.2 Study Group:

4.3.2.1 High risk clean contaminated wounds (class II) as defined with one of the following:

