6.0 Analytic Plan

6.1 Sample Size and Power

Twenty patients with a tertiary closure will be recruited (experimental group). The proportion of wound closure within 30 days for these patients will be compared to the proportion from 100 historical controls receiving a secondary wound closure. We anticipate closer to 100% of wound closure in the experimental group and closer to 0% of wound closure in the control group. Assuming the significance level at 0.05 and a two-sided test, we have greater than 90% power to claim that the proportions of wound closure within 30 days are different between the two groups.

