6.3 Analysis of Primary Outcome

The chi-squared test will be used to compare the proportions of wound closure within 30 days between the experimental group (i.e., patients receiving a tertiary wound closure) and the historical control group (i.e., patients receiving a secondary wound closure). Logistic regression models will be used when confounding variables such as age will be adjusted. Wound closure status is the outcome measure. Experimental group is the covariate of interest.

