6.4 Analysis of Secondary Outcomes

6.4.1 The analysis approach for comparing the proportion of acute and chronic wound infection between the two groups is the same as that specified in 6.3.

6.4.2 The distribution of length of stay will be examined and transformed if needed. To compare the length of stay between the two groups, the 2-sample t-test will be used if the length of stay is normally distributed and the Wilcoxon rank sum test will be used if it is not normally distributed. To adjust for confounding variables, a linear regression model will be used if the length of stay is normally distributed and a negative binomial model will be used if it is not normally distributed.

6.4.3 The analysis approach for comparing the proportion of patients that return within 30 days of surgery between the two groups is the same as that specified in 6.3.

6.4.4 Descriptive statistics, including mean, standard deviation, median, and interquartile range, will be calculated to describe the quality of life in patients receiving a tertiary wound closure,

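### The infection comparison in Section 6.4.1 does not commit to accounting for wound class, so a difference in class mix alone can bias it in either direction

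*Combined protocol and SAP*

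**What the plan says.** Section 6.3 sets a chi-squared test for the primary outcome and adds: "Logistic regression models will be used when confounding variables such as age will be adjusted". It gives no covariate list and does not say when adjustment applies. Section 6.4.1 carries this over to infection: the approach for "comparing the proportion of acute and chronic wound infection between the two groups is the same as that specified in 6.3".

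On wound class, Section 1.0 says: "As noted with an increase in the class there is an increase in the potential for infection". Its second classification table gives infection rates of 5-6% (clean contaminated), 20-25% (contaminated) and 30-40% (dirty).

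Section 3.1 admits high-risk class II, class III and class IV wounds, and Section 4.3.2 defines the study group by the same three classes. There is no quota, matching or stratification by class. The Surgery Form (Appendix E, item 5) records class for study patients.

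For controls, Section 2.1.1 says "We will identify 20 patients with characteristics described in the inclusion criteria of this study" and names postoperative clinic notes as the source of the closure data. It does not list wound class as an item to abstract.

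**The concern.** The groups are not randomised. Shared eligibility criteria make the range of classes the same in both groups, but not the proportions. Wound class is the one factor for which the protocol quantifies infection risk by level, and the gradient is steep: about six-fold from class II to class IV at mid-range (35 / 5.5 = 6.4).

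If the class proportions differ, the unadjusted test compares case mix as well as closure technique. A logistic model adjusted for age alone would remove class imbalance only so far as class tracks age. An ineffective technique could look protective, or a useful one harmful.

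**Working it through.** **The plan's own figure.** Section 6.1 claims more than 90% power for 30-day closure with 20 v 100 patients at two-sided 0.05, expecting rates near 100% and near 0%. Exact values are not given. By exact binomial enumeration of the uncorrected chi-squared test, power is about 100% at 90% v 10%, 99.98% at 80% v 20%, and 93% even at 70% v 30%. The claim reproduces and is not in question here.

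**Inputs for infection**
- Class rates: midpoints of the Section 1.0 table, 5.5% (II), 22.5% (III) and 35% (IV).
- Group sizes: 20 tertiary patients; 100 controls (Section 6.1) or 20 controls (Section 2.1.1). Both are run because the sections disagree.
- Class mixes: assumed, except the earlier tertiary series in the Section 1.0 abstract (four class III, two class IV, no class II).
- Treatment effect: none.

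**Formula.** Expected infection in a group = sum over classes of (class share × class rate).

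- 60/20/20: 0.6×5.5 + 0.2×22.5 + 0.2×35 = 14.80%
- 40/30/30: 0.4×5.5 + 0.3×22.5 + 0.3×35 = 19.45%
- 70/20/10: 0.7×5.5 + 0.2×22.5 + 0.1×35 = 11.85%
- 30/40/30: 0.3×5.5 + 0.4×22.5 + 0.3×35 = 21.15%
- Half III, half IV: 0.5×22.5 + 0.5×35 = 28.75%
- Earlier series: (4/6)×22.5 + (2/6)×35 = 26.67%

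The rejection rate is the exact probability that the two-sided 0.05 uncorrected chi-squared test declares a difference.

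| Tertiary v control mix (II/III/IV) | Expected infection | Difference (points) | Rejects, 20 v 100 | Rejects, 20 v 20 |
|---|---|---|---|---|
| 50/30/20 in both | 16.5% v 16.5% | 0 | 4.9% | 5.0% |
| 60/20/20 v 40/30/30 | 14.8% v 19.45% | −4.65 | 5.5% | 6.7% |
| 70/20/10 v 30/40/30 | 11.85% v 21.15% | −9.3 | 12% | 12% |
| All II v half III, half IV | 5.5% v 28.75% | −23.25 | 69% | 53% |
| Earlier series v 70/20/10 | 26.67% v 11.85% | +14.8 | 42% | 22% |

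**Sensitivity to the table's ranges.** For 70/20/10 v 30/40/30, the low ends give 10.5% v 18.5% (−8.0 points) and the high ends 13.2% v 23.8% (−10.6 points).

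**Sensitivity to class II risk.** If high-risk class II infection is assumed to be 10% or 15% instead of 5.5%, rejection at 20 v 100 falls from 12% to 8.6% or 6.4% for the moderate mix, and from 69% to 43% or 22% for the extreme mix.

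**Does stratifying help?** In the moderate scenario, class II is 5.5% in both groups. Within III/IV, tertiary is (0.2×22.5 + 0.1×35)/0.3 = 26.67% and control is (0.4×22.5 + 0.3×35)/0.7 = 27.86%. The 9.3-point difference shrinks to 0 and 1.2 points within strata.

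**How many covariates can be carried.** Across these mixes, expected infections among 20 tertiary patients run from 20×0.055 = 1.1 to 20×0.2667 = 5.3. That supports very few covariates, so their order of priority matters.

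**The case against.** The case on the other side is substantial, and much of it stands.

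- **Age is only an example.** Section 6.3 does not exclude wound class, and Section 6.4.2 speaks of confounders in the plural. A reader might infer that the plan prescribes an age-only model; it does not. What remains is that no covariate set is fixed, adjustment is conditional, and the strongly graded factor in the protocol's own table is not named.
- **Direction.** A reader might infer that the bias favours tertiary closure, for instance because surgeons left the worse wounds open in controls. The documents do not support this. The only tertiary case mix they report is entirely class III and IV, which points the other way.
- **Size.** The mixes are assumptions, and the mild one leaves the error rate near nominal. The 5-6% rate is also probably too low here: the same table row lists primary closure, which neither group receives, and Section 1.0 says of class II that "there are a subset of patients in which there are factors that increase the risk of SSI above baseline". A higher class II rate shrinks the effect, as shown.
- **Reach.** A reader might extend the point to the primary outcome or to return within 30 days. With closure anticipated near 100% v near 0%, nothing here threatens the primary conclusion. The documents give no return rates by wound class.
- **Largest predictor.** Section 1.0 lists other risk factors without rates by level, so wound class cannot be called the largest predictor, only the one that is quantified.

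**Conclusion.** The concern holds for the infection comparison. The plan does not commit to accounting for wound class, although its own table shows a steep gradient and the Surgery Form collects class. Class mix alone can bias the estimate in either direction.

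Under the assumed mixes, the spurious difference runs from about 5 to 23 points in favour of tertiary closure, or about 15 points against it with the earlier series' mix. False rejection runs from near nominal (5.5%) to 69% at 20 v 100, and from 6.7% to 53% at 20 v 20. These figures rest on mid-range rates from a general table that is not specific to closure method, and on mixes that the documents do not give. They show what is possible, not what will happen.

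This is a secondary outcome. The primary closure conclusion and its power statement stand.

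**What to change.** 1. In Section 6.4.1, make the main infection comparison stratified by or adjusted for wound class (II v III/IV), by Mantel-Haenszel, exact stratified or penalised logistic analysis. Put class ahead of age because few infections are expected.
2. List wound class as an item abstracted for historical controls.
3. Tabulate wound class by group, with III and IV shown separately. This shows whether the groups overlap enough for a within-class comparison and how much imbalance a two-level factor leaves.

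The cost is a small loss of precision and one more abstracted item. Class should in any case be needed to confirm that a control meets the inclusion criteria.

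Separately, the sponsor should reconcile two inconsistencies:
- The control count: Section 6.1 uses "the proportion from 100 historical controls receiving a secondary wound closure", while Section 2.1.1 has 20.
- The cut-offs for high-risk class II: Section 1.0 lists ASA above 2 and subcutaneous depth of at least 3 cm among its risk factors, while Section 4.3.2.1 uses ASA 2 or above and at least 4 cm. Whichever set is adopted should apply to both groups.

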6.4 Analysis of Secondary Outcomes

6.4.1 The analysis approach for comparing the proportion of acute and chronic wound infection between the two groups is the same as that specified in 6.3.

6.4.2 The distribution of length of stay will be examined and transformed if needed. To compare the length of stay between the two groups, the 2-sample t-test will be used if the length of stay is normally distributed and the Wilcoxon rank sum test will be used if it is not normally distributed. To adjust for confounding variables, a linear regression model will be used if the length of stay is normally distributed and a negative binomial model will be used if it is not normally distributed.

6.4.3 The analysis approach for comparing the proportion of patients that return within 30 days of surgery between the two groups is the same as that specified in 6.3.

6.4.4 Descriptive statistics, including mean, standard deviation, median, and interquartile range, will be calculated to describe the quality of life in patients receiving a tertiary wound closure,

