5.2 Secondary Outcomes

- 5.2.1 The proportion of SSI using a tertiary closure technique compared to historical controls receiving a secondary wound closure.
- 5.2.2 The length of stay as defined by the time from surgery to discharge as compared to historical controls receiving a secondary wound closure.
- 5.2.3 The proportion of patients that return within 30 days of surgery.
- 5.2.4 The quality of life in patients receiving a tertiary wound closure. It is expected that tertiary closure will be superior to secondary closure. The time to closure with the tertiary approach should be much shorter. It is unknown if wounds closed in a tertiary manner will remain closed. That was our rationale for choosing wound closure at 30 days as the primary endpoint. Differences in quality of life between the two approaches are also unknown. We have submitted an abstract from a chart review of 5 patients who have undergone tertiary closure. We are looking to expand this cohort of patients to generate more quantitative data.

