10.0 Adverse Events List and Reporting Requirements

10.1 Adverse Event List for Tertiary Closure

10.1.1 Infection

As a result of enrollment onto this trial, there is a risk of developing a wound infection. This infection could be minor (skin redness). A wound infection could also involve the deeper tissues underneath the skin. If that occurs, the incision is typically re-opened and the deeper tissues are cleaned, irrigated and packed with a dressing. Rarely, a serious wound infection causes you to develop a fever or generalized infection. Treatment of a more serious wound infection could involve the following: re-admission to the hospital, intravenous antibiotics or additional surgery.

Enrolled patients will be at medium to high risk for wound complications in general. Wound complications usually occur within the first 30 days of surgery. Incisional hernia is a more "long-term" complication of a surgical wound. This complication can occur up to 1 year after surgery. Enrolled patients will be monitored carefully for wound complications using our standard care approach for patients with medium to high risk for wound complications.

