Appendix F - Wound Form

Visit: 2 weeks 4 weeks 3 months

Date of encounter (mm/dd/yyyy): ____/____/_____

1. Infection: Yes No

If yes, date infection occurred: (mm/dd/yyyy): ____/____/_____

2. Did Wound Dehiscence occur? Yes No

If yes, date: (mm/dd/yyyy): ____/____/_____

Physician's assessment of why dehiscence occurred:

3. Percentage of wound healing: _____%

4. Day of hospital discharge (mm/dd/yyyy): ____/____/_____

5. Post-surgery date wound is closed

(mm/dd/yyyy): ____/____/_____

6. Is the wound closed on POD # 30? Yes No

7. Wound Complications (free text):

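### The infection comparison in 6.4.1 has no common window, definition or ascertainment rule for tertiary patients and historical controls

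*Combined protocol and SAP*

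**What the plan says.** **Name of the outcome.** Objective 2.2.1 and analysis section 6.4.1 refer to acute and chronic wound infection; 6.4.1 speaks of "comparing the proportion of acute and chronic wound infection between the two groups". Outcome 5.2.1 names it differently: "The proportion of SSI using a tertiary closure technique". Acute and chronic are not defined.

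**Tertiary group.** Appendix F is completed at scheduled visits, "Visit: 2 weeks 4 weeks 3 months", and the activities table in 4.2 allows 5 days either side. The form has one Yes/No infection item and a date of occurrence. It has no criteria and no acute/chronic field.

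**Controls.** They are laparotomy patients from calendar year 2018. The only control data source named is in 2.1.1: "We will be able to abstract this information from the postoperative clinic visit notes". The sentence before it is about time to wound closure, so that is the information meant.

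**Analysis.** 6.4.1 borrows the method of 6.3: a chi-squared test, with logistic regression for adjustment. The 30-day limit in 6.3 is attached to closure.

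**Definition.** Section 6.2.1 defines a wound infection by skin erythema, purulent drainage, nonviable or necrotic subcutaneous tissue, or a positive culture. It does so for the interim safety rule, and neither 5.2.1, 6.4.1 nor Appendix F refers to it.

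**The concern.** A two-group comparison of proportions is interpretable only if an event has the same chance of being counted in each group. Here one group has a dated form completed prospectively up to 3 months, and the other has whatever a retrospective record holds, for a length of time the plan does not state. Any observed difference would mix the effect of the closure technique with the way infections were found.

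Infection is the first secondary objective, and SSI is the trial's opening rationale. An ascertainment difference could make one technique look worse without cause. It could also hide a real difference: if tertiary closure truly halved infection from 25% to 12.5%, and control records held only half of control infections, both observed proportions would be 12.5%.

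**Working it through.** **1. Is a window inherited from elsewhere?** The three compared proportions, side by side:

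| Outcome | Window in the text |
|---|---|
| Wound closure (5.1.1, 6.3) | 30 days |
| Return after surgery (5.2.3, 6.4.3) | 30 days |
| Infection (2.2.1, 5.2.1, 6.4.1) | none |

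Section 6.4.3 also borrows the method of 6.3, yet restates its own 30 days. Borrowing the method therefore does not appear to carry the window with it. Section 7.0 lists a 30-day follow-up form, but the contents page has no such appendix (Appendix G is the SF-36), so that entry does not fix an infection window either.

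**2. The plan's own figure.** The only power statement, above 90% in 6.1, concerns closure. With "Twenty patients with a tertiary closure will be recruited (experimental group" and "the proportion from 100 historical controls receiving a secondary wound closure", the normal approximation gives about 1.00 at 90% versus 10% closure and 0.934 at 70% versus 30%, so it reproduces. No power is stated for infection.

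**3. Size of a spurious gap (illustration).** Inputs:
- True risk *p*, equal in both groups: 25%, the top of the 20–25% background range for contaminated wounds in Section 1.0.
- Fraction of control infections missed, *m*: 10% to 40%. This is an assumption; the documents give no value.

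Spurious gap = *p* − *p*(1 − *m*) = *p* × *m*:
- *m* = 10%: 0.25 × 0.10 = 0.025, or 2.5 points
- *m* = 20%: 0.25 × 0.20 = 0.05, or 5 points
- *m* = 40%: 0.25 × 0.40 = 0.10, or 10 points

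If infections were missed in the tertiary group instead, the gap would have the same size and the opposite sign.

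**4. Effect on the test.** Exact enumeration of the uncorrected chi-squared test, two-sided 0.05, 20 tertiary patients, true risk 25% in both groups. Both control counts are shown because 6.1 says 100 while 2.1.1 says "We will identify 20 patients with characteristics described in the inclusion criteria of this study".

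| Control infections missed | Observed control risk | P(p < 0.05), 100 controls | P(p < 0.05), 20 controls |
|---|---|---|---|
| 0% | 25% | 0.05 | 0.05 |
| 10% | 22.5% | 0.06 | 0.05 |
| 20% | 20% | 0.10 | 0.07 |
| 40% | 15% | 0.23 | 0.12 |

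**5. How much is window and how much is detection?** Section 10.1.1 says "Wound complications usually occur within the first 30 days of surgery". If so, few infections would be lost merely because control notes end early, and the window-only part lies near the 2.5-point end. The rest would come from differences in definition and in prospective versus retrospective recording, which the timing remark does not limit.

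**The case against.** The strongest reply is that the plan is silent, not demonstrably biased, and much of that stands.

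- **Control source and window.** A reader might infer that control infections come from clinic notes and that their window is shorter. The documents say neither. The clinic-note sentence concerns closure, and control follow-up length is never given. Chart abstraction is a reasonable expectation for a retrospective cohort, but no more than that.
- **Active versus passive search.** A reader might infer that tertiary patients are searched more intensively. Sections 4.3.4.2 and 10.1.1 describe their monitoring as standard care. What differs on the page is the recording: a dated form at fixed visits.
- **Direction.** A reader might infer that controls must look better. Section 6.1 expects almost no control wounds closed by day 30, and Section 1.0 describes secondary closure with dressing changes 2–3 times daily or VAC changes 2–3 times weekly. Open wounds may be inspected more often and documented for longer, so the sign is open.
- **Precision.** At 25% risk the 95% half-width for the difference is 1.96 × √[0.25 × 0.75 × (1/20 + 1/100)] = 21 points with 100 controls, and 27 points with 20. The illustrated gaps are smaller than this. That limits what the comparison can show, but it does not remove a systematic error.
- **Is SSI undefined?** Section 1.0 introduces an SSI classification whose content is missing from the text as read. It would be unsafe to say the protocol nowhere classifies SSI. The point is that the infection outcome and its analysis are not tied to any definition.

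None of this supplies the missing window, definition or control rule.

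**Conclusion.** The concern holds as one of unspecified and unaligned ascertainment. Run as written, 6.4.1 sets form-recorded infection up to 3 months against an undefined control record, under two outcome names and with no definition linked to the analysis. Unequal ascertainment is likely and the plan has nothing to prevent it. That the windows are in fact unequal, or that the bias favours a particular group, is not established.

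The illustrative size is 2.5 to 10 points at an equal true risk of 25% with 10% to 40% of control infections missed. It rests on an assumed miss fraction and a background rate by wound class, not on trial data. This affects a secondary outcome and leaves the primary closure comparison untouched. It should be corrected before control abstraction begins.

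**What to change.** 1. In 2.2.1, 5.2.1 and 6.4.1 use one outcome name and one written definition. The wound-infection definition in 6.2.1 is a candidate.
2. Compare infections with onset by postoperative day 30 in both groups. For tertiary patients use the infection date on Appendix F, whichever visit recorded it: the 4-week visit can fall anywhere from day 23 to day 33 (28 ± 5), so onset date and not visit should decide.
3. For controls, abstract the same items under the same definition from the chart, in patients with documented follow-up to day 30. Report how many controls lack it.
4. As a sensitivity analysis, abstract tertiary infections from routine notes by the control rule, so that both groups are read from the same kind of source.
5. Report later (chronic) tertiary infections to 3 months descriptively, and state the remaining prospective-versus-retrospective difference as a limitation.

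**Cost.** Wording in three sections, an abstraction rule for controls, and a second chart reading for 20 tertiary patients. No new visit or form item is needed. Late infections are described and not compared, so objective 2.2.1 must be reworded to match. Requiring follow-up to day 30 may also drop some controls.
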